8.2.1 Snellen visual acuity test

A Snellen Eye Chart will be used to assess visual acuity for distance vision. Visual Acuity will be conducted using the subject's best distance correction (e.g. contacts or eye glasses) at a distance of approximately 6 feet from the chart. Each eye will be measured separately by either using an occluder or having the subject cover each eye. The subject will be asked to start reading the letters at the top of the chart working their way to the bottom. The smallest row of letters that the subject can read will indicate their visual acuity listed on the chart. Snellen Visual Acuity will be recorded in their source documentation and eCRF. If there is one or more visual acuity line changes during the course of study, these should be reported to the Sponsor within 24 hours of awareness as an AESI. These events should be reviewed and assessed by the Investigator as an Adverse Event.

8.2.2 Extraocular muscle function test

Extraocular muscle function testing examines the function of the eye muscles. This test observes the movement of the eyes in six specific directions to evaluate weakness or other problem in the extraocular muscles. The subject will be asked to sit or stand with their head up and looking straight ahead. The assessor will hold a pen or other object approximately 16 inches in front of the subject's face. The assessor will then move the object in several directions and ask the subject to follow it with their eyes, without moving their head. Normal or Abnormal will be recorded in the source documentation and eCRF. Changes in movement of the eyes during the course of the study should be reviewed and assessed by the Investigator for a potential Adverse Event.

	Title 43USTT1904 CSP Infraorbital Hollows	Doc id MA-40833
--	---	---------------------------

Effective date: 2021-12-15 20:29

8.2.3 Confrontation visual field

The Confrontation Visual Field test will be used to assess the subject's peripheral vision. The examiner will sit facing the subject, about 3 to 4 feet away from the subject and ask the subject to fix their gaze on the examiner's eye. The examiner will hold their arms straight out to the side and bring their hands into the subject's visual field from the sides in each quadrant. The subject will signal as soon as the hand is seen. Each quadrant will be recorded as normal or abnormal in the source documentation and eCRF. Changes in the visual field of the eyes during the course of the study should be reviewed and assessed by the Investigator for a potential Adverse Event

8.3 Subject Diary Data

The subject shall evaluate local tolerability in a 28 days diary, starting on the day of each treatment. The presence and maximum intensity of pre-defined, expected post-treatment events, i.e. bruising, redness, pain, tenderness, lumps/bumps, itching and swelling shall be assessed for the treated area. The Subject Diary will also have an area for the subject to report any other symptoms outside the pre-identified. Especially symptoms like change in vision change in skin color or crusty/scabby skin around the eyelids, dizziness, confusion, weakness or numbness in arms or legs, changes to consciousness or alertness, difficulty speaking/speech impairment, face droop, headache and fever should be recorded. The diary will also include instructions for the subject to:

- Contact an eye doctor (retinal specialist or ophthalmologist) if they experience change in vision (i.e. vision loss, blurriness, double vision, pain in or around eye, blindness, blind spots, problems moving your eyes), change in skin color or crusty/scabby skin around the eyelids
- Call 911 and seek immediate medical attention if signs of stroke or subject experience dizziness, confusion, weakness or numbness in face, arms or legs, changes to consciousness or alertness, difficulty speaking/speech impairment, face droop

The Investigator or study staff should review the diary for completion and clarify any events as needed. For events that are ongoing at the time of diary completion, the Investigator should follow them and record resolution in the subject's study file and eCRF. Diary data will be analyzed and displayed separately from AE data.

CCI

8.4 Laboratory assessments

Pregnancy Test

For all women of childbearing potential, including those currently using contraception, a urine pregnancy test is required prior to receiving any study treatment (Day 1, optional touch-up, or o treatment). **The test result must be negative for the subject to receive any treatment with study product.** The test result will be documented in the subject's file and eCRF.

Version: 10.0

Effective

	Title 43USTT1904 CSP Infraorbital Hollows	Doc id MA-40833
--	---	---------------------------

8.5 Adverse Events

8.5.1 Definition of an Adverse Event

An AE is any untoward medical occurrence, unintended disease or injury, or untoward clinical signs (including abnormal laboratory findings) in subjects, users or other persons^I, whether or not related to the study product.

This definition includes:

- a) events related to the investigational product or the reference product
- b) events related to the procedures involved

8.5.2 Definition of a Serious Adverse Event

A Serious Adverse Event (SAE) is an AE that:

- a) led to death,
- b) led to serious deterioration in the health of the subject, that either resulted in
 1. a life-threatening^{II} illness or injury, or
 2. a permanent impairment of a body structure or body function, or
 3. in-patient or prolonged hospitalization^{III}, or
 4. medical or surgical intervention to prevent life-threatening illness or injury or permanent impairment to a body structure or a body function,
- c) led to fetal distress, fetal death, or a congenital abnormality or birth defect

In cases of doubt, whether an AE fulfils a serious criterion or not, there should be a predisposition to report as a SAE rather than not report as such (see section 8.5.7).

8.5.3 Definition of unanticipated adverse effect

An unanticipated adverse device effect is any serious adverse effect on health or safety or any life-threatening problem or death caused by, or associated with, the investigational product, if that effect, problem, or death was not previously identified in nature, severity, or degree of incidence, or any other unanticipated serious problem associated with a device that relates to the right, safety or welfare of the subject (see US requirement CFR 812.3 (s)).

8.5.4 Recording instructions

Each subject should be questioned about AEs at each study visit following signing of informed consent. The question asked should be: "Since your last clinical visit; have you had any health problems?". Information on AEs can also be obtained from signs and symptoms detected

^I For users or other persons, this definition is restricted to events related to the investigational product.

^{II} The term "life-threatening" in the definition of "serious" refers to an event in which the patient was at risk of death at the time of the event; it does not refer to an event which hypothetically might have caused death if it were more severe. (Source: ICH-E2A clinical safety data management: definitions and standards for expedited reporting).

^{III} Planned hospitalization for a pre-existing condition, or a procedure required by the CSP, without serious deterioration in health, is not considered a SAE. (Source: ISO14155:2011).

	Title 43USTT1904 CSP Infraorbital Hollows	Doc id MA-40833
--	---	---------------------------

during each examination or from a laboratory test, observations made by the study site personnel, subject diaries, or spontaneous reports from the subjects or their relatives.

When an AE is related to a device deficiency (refer to section 8.6), including technical device malfunction, the AE shall be recorded on the AE form/module in the eCRF and the technical complaint shall be reported separately on the clinical study complaint form provided separately in the Investigator file.

Investigators, or other study site personnel, shall record all AEs in the eCRF, including:

- a) Event term (recorded in standard medical terminology and avoiding abbreviations)
- b) Affected area
- c) Start date (first day with symptoms)
- d) Stop date (last day with symptoms)
- e) Intensity (mild, moderate, or severe according to definition in section 8.5.4.1)
- f) Seriousness (serious or not serious, according to definition in section 8.5.4.2)
- g) Causal relationship to study product or study product injection procedure (yes or no)
- h) Action taken (none, medication treatment, non-pharmacological treatment, or other procedures/tests, subject withdrawn)
- i) Outcome of the AE (ongoing, recovered, recovered with sequelae, death, chronic/stable, not recovered at the end of the study)

The AE form/module in the eCRF must be signed and dated by the Investigator.

The pre-defined, expected post-treatment events shall be assessed separately. These events shall be collected by direct questioning to subjects in a diary used daily for 28 days after each treatment.

8.5.4.1 Intensity

Intensity will be recorded for each reported AE. The following definitions of intensity are to be used:

Mild: Awareness of symptoms or signs, but easily tolerated (acceptable)

Moderate: Enough discomfort to interfere with usual activity (disturbing)

Severe: Incapacity to work or to do usual activity (unacceptable)

If the intensity changes within one day, the maximum intensity of the AE during that day shall be recorded.

8.5.4.2 Causal relationship and seriousness

Each AE, serious as well as non-serious, shall be assessed by the Investigator for causal relationship with the study product and its use (the injection procedure) and for seriousness (Yes or No) of the event.

A two-point scale (Yes or No response) shall be used for the causality assessments. The Investigators shall be asked to indicate a response to each of the following questions in the eCRF:

	Title 43USTT1904 CSP Infraorbital Hollows	Doc id MA-40833
--	---	---------------------------

- “Do you consider that there is a reasonable possibility that the event may have been caused by the study product?”, and
- “Do you consider that there is a reasonable possibility that the event may have been caused by the study product injection procedure?”

If any of these questions is answered Yes, the AE is considered related.

Each AE will also be assessed for causal relationship and seriousness by the Sponsor, in order to fulfil regulatory requirements.

8.5.5 Reporting of Adverse Events

Adverse Event reporting on each subject shall start once a subject is enrolled (i.e., randomized and/or treated) in the study. All other events that occur after the subject signs the ICF but before enrollment will be recorded in the subject’s medical history. The reporting shall continue during each follow-up visit (including telephone contacts and extra visits between planned visits) until the last scheduled visit in the study.

All AEs, non-serious as well as serious, are to be reported as an AE in the eCRF.

8.5.6 Reporting of Adverse Events of special interest (AESIs)

AESIs should be reported (using the AE Clarification Form) within 24 hours of awareness to the Sponsor at the email address [contact]. In case of difficulty to obtain all the required information within 24 hours, an initial report can be submitted with follow up information provided within 24 hours of awareness of the new information.

The following information should be provided when reporting an AESI:

- Subject identification (subject number and initials)
- Event description including observed symptoms
- Medical history related to event
- Event onset date and time
- Depth of injections
- Interventions implemented to treat event
- Event outcome (with resolution date and time if applicable)
- Relatedness to study product or procedure
- Seriousness of event
- Study treatment information (number of injections, date of injections, name of product injected, volume injected, etc.)

If the Investigator assesses an AESI to be serious, an SAE report should be submitted as specified in section 8.5.7.

Upon receipt of the AESI report, the Medical Monitor and Sponsor will review the information provided, assess the event, and report to RA within 24 hours and to the IRB as applicable.

Effective date: 2021-12-15 20:29

Effective

Version: 10.0

	Title 43USTT1904 CSP Infraorbital Hollows	Doc id MA-40833
--	---	---------------------------

8.5.7 Reporting of serious Adverse Events

The Investigator shall report any **SAE** to the Sponsor **immediately but not later than 24 hours of awareness of the event**. This initial report can be made via e-mail or submitted via the eCRF.

In case of difficulty to obtain all the required information within 24 hours, an initial report can be submitted, with the following information as a minimum, irrespective of whether some of it is regarded as preliminary:

- Subject identification (age, gender, initials, subject number)
- Adverse Event description
- Date when AE occurred
- Name of PI
- Name of study product

Follow-up information and data missing in the initial SAE reporting shall be gathered as soon as possible and reported to the Sponsor immediately but not later than 24 hours of awareness of the new data. Complete and adequate information on each SAE is required. All attempts to obtain this information, including dates for follow-up activities, must be documented by the Investigator.

Supporting documentation to be provided with the SAE report:

- Concomitant therapies form/list
- AE form/list
- Medical history form/list
- Any other relevant supporting documentation (e.g. hospital notes, death certificate, autopsy reports etc.)

E-mail for SAE reporting: [contact]

E-Fax number for SAE reporting: [contact]

For non-urgent complementary information that is not possible to send by e-mail or fax, please use surface mail.

Surface mail for providing complementary information: Advanced Clinical
ATTN: Pharmacovigilance and Safety Monitoring
[name]
[name]
[name]
United Kingdom

Effective date: 2021-12-15 20:29

Effective

Version: 10.0

 GALDERMA <small>EST. 1981</small>	Title 43USTT1904 CSP Infraorbital Hollows	Doc id MA-40833
---	---	---------------------------

Effective date: 2021-12-15 20:29

The SAE form must be signed and dated by the Investigator. If the initial 24-hour SAE report does not contain full information or if it is made without using the SAE form the fully completed and signed SAE form shall be e-mailed or faxed to the Sponsor. A copy of the fully completed SAE form shall be kept at the site. The blinded evaluator should perform live effectiveness assessments only and not discuss the treatment or any potential Adverse Events with the patient.

In addition, the PI shall report SAEs to the responsible IRB without undue delay. The PI is responsible for checking what reporting procedures are applicable for his/her IRB regarding SAEs and final report of the outcome of the study and to comply with such reporting procedures during the study period.

The Sponsor is responsible for reporting to the RA, if applicable and according to national regulations.

8.5.8 Stopping Rule

Enrollment and treatment into the study will be temporarily halted if the Sponsor receives a SAE for a vascular embolic event that lead to skin necrosis, vision loss, or stroke and is determined by the Investigator to be directly or possibly related to the study device or injection procedure. The SAE will be investigated by the Sponsor. If the Sponsor's investigation concludes:

- The SAE was unanticipated, directly related to the study product or device injection procedure, and presents an unreasonable risk to study subjects, the study will be terminated and the Investigators notified. The IRB and RA will also be notified if the study is prematurely terminated due to safety concerns.
- If the SAE does not meet the above criteria, then enrollment in the study will continue.

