Lidocaine can, in rare cases, give allergic reactions, and therefore subjects with known allergy or hypersensitivity to local anesthetics should not be included in the study.

Additional information about reported AEs and anticipated risks are included in the product specific IFUs and ROPI.

To mitigate these risks, only study Investigators qualified by education and experience, and who are skilled in the use of dermal fillers from their clinical practice and involvement in clinical research, and with a firm knowledge of the vascular anatomy and understanding of the depth and plane of injection as well as knowledge of the signs and symptoms and management of potential complications will be chosen in order to assure proper device implantation and management of study risk. Visual function assessments will be performed before and after gel injection; an Intravascular Treatment Protocol is available for reference would an intravascular event occur; and the subject diary includes instructions in case of severe intravascular events. The study protocol also defines a stopping rule, see section 8.5.8.

Based on the open-label clinical studies sponsored by the company as well as published literature and spontaneously reported Adverse Events from the market, it is concluded that there is reasonable assurance from a safety perspective for conducting an IDE clinical trial in the USA, using *Restylane-L* for injection into the infraorbital hollow (tear trough) area in subjects over the age of 21.

Given the anticipated low level of transient and acceptable AEs in connection with the injection, the protocol required safety assessments, and the training being provided on the injection technique, it was determined the risk-benefit assessment for use of *Restylane-L* for correction of infraorbital hollows offer a clinical benefit at reasonable risk.

3. Objective(s) and Endpoint(s)

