8.5.13 Anticipated Adverse Events

Information regarding anticipated AEs for *Restylane-L* is included in the study specific IFU.

8.6 **Device deficiencies**

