important intellectual content; and (3) final approval of the version to be published; and (4) agreement to be accountable for all aspects of the work in ensuring that questions related to the accuracy or integrity of any part of the work are appropriately investigated and resolved^V. Conditions 1, 2, 3, and 4 must all be met in order to be designated as author. Those who do not meet all four criteria will be acknowledged. Among the authors that fulfil the above mentioned criteria, one author will be appointed by Q-Med AB to take primary responsibility for the overall work as primary author.

15. Suspension or Premature Termination

The Sponsor will suspend or terminate the study when so instructed by the IRB or RA, or if it is judged that the subjects are subjected to unreasonable risks, or for valid scientific or administrative reasons, or for business reasons.

The Sponsor may also decide to close a single study site due to unsatisfactory subject enrolment or non-compliance with the CSP, GCP, or applicable regulatory requirements.

In the event of premature termination, Q-Med AB will provide information on the handling of currently enrolled subjects who have not completed the study.

Effective

Version: 10.0

^V Defining the role of authors and contributors, compiled by the International Committee of Medical Journal Editors (ICMJE) (<http://www.icmje.org>).

GALDERMA <small>EST. 1981</small>	Title 43USTT1904 CSP Infraorbital Hollows	Doc id MA-40833
---	---	---------------------------

Effective date: 2021-12-15 20:29

16. References

2. Fitzpatrick T.B. (1988). The validity and practicality of sun-reactive skin types I through VI. *Arch. Dermatol.* 124, 869–871.

Effective

Version: 10.0

	Title 43USTT1904 CSP Infraorbital Hollows	Doc id MA-40833
--	---	---------------------------

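### After a safety halt, Protocol 8.5.8 can tell the Sponsor to continue enrollment where Section 15 requires suspension or termination

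*Protocol*

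**What the plan says.** Protocol 8.5.8 works in two steps.

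- **Halt.** "Enrollment and treatment into the study will be temporarily halted if the Sponsor receives a SAE" for a vascular embolic event with one of three outcomes (skin necrosis, vision loss, stroke) that the Investigator judges directly or possibly related to the device or the injection.
- **Exit.** The Sponsor investigates. The study is terminated if the investigation concludes: "The SAE was unanticipated, directly related to the study product or device injection procedure, and presents an unreasonable risk to study subjects". For every other conclusion the text reads: "If the SAE does not meet the above criteria, then enrollment in the study will continue". There is no third route, such as keeping the halt in place.

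Protocol Section 15 sets the general rule. "The Sponsor will suspend or terminate the study when so instructed by the IRB or RA", and the same sentence adds "or if it is judged that the subjects are subjected to unreasonable risks" as a further sufficient reason. It does not ask whether the event was anticipated or how it was related.

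The synopsis gives the halt and the Sponsor's investigation but no exit criteria, so it does not settle the matter. Neither section says which one prevails.

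**The concern.** The exit test is narrower than both the trigger and the general rule. It adds a requirement that the event be unanticipated, which neither of the others has, and it accepts only a direct relation although the trigger also accepts a possible one. The Sponsor could therefore conclude that subjects face unreasonable risk and still be told by the section written for that situation to continue, while Section 15 tells it to stop or suspend.

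At stake is whether the study goes on after an embolic injury near the eye. Injections are possible at baseline, at month 1 and at month 12, so the exit rule bears on more than first treatments. Protocol 10.9 provides for no data monitoring committee, and the investigation under 8.5.8 is the Sponsor's own. Two mandatory instructions that disagree should not have to be reconciled during a halt.

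**Working it through.** No figure in the plan is in question. The check is to read 8.5.8 as a decision table and set it against Section 15.

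**Step 1: the table.** The exit test uses three yes/no findings: unanticipated, directly related, unreasonable risk. That gives 2 × 2 × 2 = 8 combinations. Because all three are required, 1 leads to termination and 8 − 1 = 7 lead to continue.

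**Step 2: the cells that Section 15 covers.** Fix unreasonable risk at yes. This leaves 2 × 2 = 4 combinations, and Section 15 requires action in all 4.

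| Class of event | Relation found by the Sponsor | 8.5.8 now | Section 15 | If only the unanticipated condition were deleted |
|---|---|---|---|---|
| Unanticipated | Direct | Terminate | Suspend or terminate | Terminate |
| Unanticipated | Not direct (e.g. possible) | Continue | Suspend or terminate | Continue |
| Anticipated | Direct | Continue | Suspend or terminate | Terminate |
| Anticipated | Not direct (e.g. possible) | Continue | Suspend or terminate | Continue |

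8.5.8 agrees with Section 15 in 1 of 4 cells and contradicts it in 4 − 1 = 3. Deleting only the unanticipated condition would still leave 2 of 4 in contradiction, because the requirement of a direct relation remains.

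**Step 3: can the contradictory cells occur?**

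- *Possibly related.* Yes, on the face of the text. A possible relation starts the halt, but it cannot satisfy the exit test.
- *Anticipated.* Possible, but not automatic. Section 2.4 already reports ischemia with necrosis, blindness or visual loss, and cerebral infarction after facial filler or other facial aesthetic treatment. Those are 3 of the 3 outcomes that trigger the halt, and periorbital areas are named for the vascular occlusions. Section 2.4 also says: "Additional information about reported AEs and anticipated risks are included in the product specific IFUs and ROPI". Its next paragraph, on mitigating risk, ends: "The study protocol also defines a stopping rule, see section 8.5.8".
- *Limits on that.* Section 8.5.3 defines an unanticipated device effect as one not identified beforehand in nature, severity or degree of incidence, so a known type of event may still qualify as unanticipated. Section 8.5.8 does not cite that definition; applying it is an assumption. Under 8.5.13 the information on anticipated AEs "is included in the study specific IFU", which is not among the documents.

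**Step 4: treatment.** The halt covers enrollment and treatment, but the continue bullet names enrollment only. Read literally, it does not say whether injections resume. Adding treatment to that bullet is safe only once the bullet is limited to events without unreasonable risk; otherwise it would expressly restart injections in the contradictory cells.

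**The case against.** The strongest reply is that the case is narrow and already covered. Section 2.4 weighed the known vascular risks and judged the overall risk reasonable. An event that tips the balance would often do so by being more severe or more frequent than expected, and 8.5.3 would then make it unanticipated. Section 15 is mandatory and unqualified, so 8.5.8 can be read as the exit from one particular halt, with Section 15 governing any judgment of unreasonable risk. There are also outside checks: Investigators report SAEs to the IRB (8.5.7), the Sponsor reports events of special interest to the regulator within 24 hours (8.5.6), and either body can order suspension or termination.

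Much of this stands, and it limits the reach of the point. It does not remove the contradiction. 8.5.8 is not silent on these cases; it says to continue. The argument about severity and incidence also does nothing for an event found only possibly related.

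Three stronger readings are tempting but unsupported:

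- *The plan leaves no power to stop.* Section 15 and the IRB and regulator routes say otherwise.
- *The stopping rule does nothing for known risks.* The halt has no anticipation condition; every qualifying SAE stops enrollment and treatment and is investigated. Only termination under 8.5.8 carries that condition.
- *The trigger events are bound to be classed as anticipated.* Section 2.4 shows that the types of event are known, largely for fillers in general. It does not show how a given event would be classified.

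**Conclusion.** The point holds as a conflict between two rules. In 3 of the 4 combinations with unreasonable risk, 8.5.8 directs continued enrollment where Section 15 requires suspension or termination. These are logical cells; the documents give no event rate, and none is claimed. The conclusion rests on reading the three exit criteria as jointly required and the second bullet as covering everything else, which is how they are written. How often the anticipated cell would arise depends on Sponsor judgment and on the unseen IFU, so confidence in the practical reach is moderate. It should be corrected: the rule is a safety rule, its backstops are real, and the correction is cheap.

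**What to change.** Reword the exit part of 8.5.8 and leave the trigger unchanged.

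- **First bullet.** If the Sponsor concludes that the SAE presents an unreasonable risk to subjects and was directly or possibly related to the product or its injection, then, whether or not it was anticipated, the study is suspended or terminated in accordance with Section 15 and the Investigators are notified. The IRB and regulator are told of a suspension for safety as well as of a termination.
- **Second bullet.** If the Sponsor concludes that the SAE does not present an unreasonable risk, enrollment and treatment continue. In any conflict, Section 15 governs.

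With this wording none of the 4 unreasonable-risk cells leads to continue. If the Sponsor finds unreasonable risk but no relation at all, neither bullet releases the halt and Section 15 decides.

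The cost is an amendment to one section, with no new data, committee or analysis. The downside is that a known type of event, or one only possibly related, can now lead to suspension or termination under 8.5.8. That happens only where the Sponsor has itself concluded unreasonable risk. Section 15 already requires action there, and the choice between suspending and terminating is kept.
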